8.1.3 Exploratory Assessments

8.1.3.1 Viral Load and/or Shedding

As outlined in the SOA, OP swabs and plasma and serum will be collected on Day 1; and Days 3, 5, 8, and 11 (while hospitalized); and OP swabs and plasma and serum on Day 15 and 29 (if attends an in-person visit or still hospitalized). Samples are stored as outlined in the MOP. These assays are not developed yet, and the ability to test samples at one central lab is not clear. Therefore, while viral load/shedding is thought to be an important endpoint, considering the limitations above, it is listed as an exploratory endpoint.

OP swabs are preferred, but if these are not obtainable, nasopharyngeal (NP) or nasal swabs may be substituted. Due to limited lack of swabs and other supplies at some sites and limitations on personal protective equipment (PPE), the inability to obtain these samples are not considered protocol deviations and should be documented in the subject's record.

If virology assays can be set up with enough numbers of specimens tested, these data will be submitted as part of the Clinical Study Report (CSR). This may be submitted separately, as a supplemental CSR.

Samples collected for viral assessment may be probed for the emergence of antiviral resistance at a future date. These data, if available, may be submitted as a supplement report.

The schedule of assessments (SOA, [Section 1.3](#)) lists several research laboratory samples to be collected. It is preferred that these samples are collected and sent to the NIAID repository to be tested in one central laboratory. Current US Centers for Disease Control and Prevention (CDC)

guidance is these samples can be processed in a Biosafety Laboratory (BSL) 2 environment. However, institutions may impose restrictions on processing the samples (i.e., they may require BSL-3) or there may be restrictions on sending samples. In these circumstances, the following apply:

Blood for PCR SARS-CoV-2

- If the samples can be processed but cannot be sent to the repository, the samples may be stored locally.
- The sponsor may elect to have some or all of these samples run locally, pending confirmation of the assays to be used and the qualifications of the local laboratory. The sponsor will work with the site to determine when this could occur and how these data can be imported into the study database.
- If a BSL-3 environment is needed for processing these samples, these samples may be omitted.

Oropharyngeal, nasopharyngeal, or nasal swab

- If the samples can be processed but cannot be sent to the repository, the samples may be stored locally.
- The sponsor may elect to have some or all of these samples run locally, pending confirmation of the assays to be used and the qualifications of the local laboratory. The sponsor will work with the site to determine when this could occur and how these data can be imported into the study database.
- If a BSL-3 environment is needed for processing these samples, these samples may be omitted and documented each time omitted.

Blood for serum (for secondary research)

- If the samples can be processed and but not sent to the repository, the samples may be stored locally.
- If a BSL-3 environment is needed for processing these samples, these samples may be omitted and documented each time omitted.

8.1.3.2 Immunology Studies

As outlined in the SOA, plasma and blood will be collected on Days 1, 3, and 8 (while hospitalized) and on Days 15 and 29 (if attends an in-person visit or still hospitalized) for evaluation of cytokines, proteomic analysis of inflammation and cytokines, transcriptome analysis and PBMC assessment. Samples are stored as outlined in the MOP. If a BSL-3 environment is needed for processing of these samples, these samples may be omitted and documented each time omitted.

Transcriptome analysis and PBMC assessment involve genetic sequencing, however this study will not involve genetic tests intended to discover disease-determining genes. Study analyses could potentially result in medically relevant incidental findings. Additionally, in the future, novel disease-associated phenotypes may be discovered that might be identified in samples stored under this study. Many research laboratory tests are not certified by the Clinical

Laboratory Improvement Amendments (CLIA), so generated genetic data cannot be meaningfully interpreted outside the narrow focus of the study and will not be routinely returned to subjects or their physicians. If a clinically significant finding is discovered and a CLIA-certified test is available for confirmation, the PI (or designee) will contact the subject to inform them of the finding and counsel them on confirming the result through a clinical provider.

8.2 Safety and Other Assessments

Study procedures are specified in the SOA. A study physician licensed to make medical diagnoses and listed on the 1572 will be responsible for all trial-related medical decisions.

Physical examination:

A targeted physical examination (targeted exam details in MOP) will be performed at baseline prior to initial study product administration on Day 1. The baseline physical examination can be one that is conducted from screening to Day 1. Post-baseline physical examinations will be done only when needed to evaluate possible adverse event(s) (i.e. any new signs or symptoms). No routine physical exam is needed for study visits after Day 1.

Study staff at some sites are not allowed into the subject's rooms due to a limited supply of PPE and the need for strict respiratory isolation measures for COVID-19 patients. Because of limited access to subjects, physical exams can be performed by any licensed provider at the study hospital even if they are not study staff listed on the FDA Form 1572. The study team can extract the required information from the hospital chart or EMR.

Clinical laboratory evaluations*:

- Fasting is not required before collection of laboratory samples.
- Blood will be collected at the time points indicated in the SOA.
 - Minimal clinical safety laboratory tests include WBC, differential, Hgb, PLT, creatinine (and calculate an estimated glomerular filtration rate (eGFR); the formula used is determined by the sites, but should be consistent throughout the study), total bilirubin, AST, ALT, and INR. Additional safety laboratory tests may be required for a given stage due to the study product risk profile. See safety laboratory in the stage-specific appendix.
 - Day 1 clinical laboratory evaluations are drawn prior to initial study product administration as a baseline and results do not need to be reviewed to determine if initial study product administration should be given.
- Clinical laboratory testing will be performed at each clinical trial site in real time.

*Venipuncture volumes are listed in each stage-specific Appendix.

8.2.1 Procedures to be Followed in the Event of Abnormal Laboratory Test Values or Abnormal Clinical Findings

If a physiologic parameter (e.g., vital signs or laboratory value) is outside of the protocol-specified criteria, then the measurement may be repeated once if, in the judgment of the investigator, the abnormality is the result of an acute, short-term, rapidly reversible condition or was an error. A physiologic parameter may also be repeated if there is a technical problem with

the measurement caused by malfunctioning or an inappropriate measuring device (i.e., inappropriate-sized BP cuff).

8.2.2 Unscheduled Visits

If clinical considerations require the subject to be contacted or seen prior to the next schedule assessment to assure the subject's well-being, it is permissible in this protocol. However, no research data is collected at this visit.

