
2. To evaluate the safety of different investigational therapeutics as compared to the control arm as assessed by:
 
 ● Cumulative incidence of SAEs through Day 29. ● Cumulative incidence of Grade 3 and 4 clinical and/or laboratory adverse events (AEs) through Day 29. ● Discontinuation or temporary suspension of study product administration (for any reason). ● Changes in white blood cell (WBC) count with differential, hemoglobin, platelets, creatinine, total bilirubin, alanine aminotransferase (ALT), aspartate aminotransferase (AST), and international normalized ratio (INR) over time (analysis of lab values in addition to AEs noted above). 	
 ● Serious adverse events (SAEs). ● Grade 3 and 4 AEs. ● Episodes of early discontinuation or interruption of study product administration. ● WBC with differential, hemoglobin, platelets, creatinine, total bilirubin, ALT, AST, and INR on Day 1; Days 3, 5, 8, and 11 (while hospitalized); and Days 15 and 29 (if attends in-person visit or still hospitalized).
Exploratory	

1. To evaluate the virologic efficacy of different investigational therapeutics as compared to the control arm as assessed by:
 
 ● Percent of subjects with SARS-CoV-2 detectable in saliva (or best technology) sample at Days 3, 5, 8, 11, 15, and 29. ● Quantitative SARS-CoV-2 virus in saliva (or best technology) sample at Days 3, 5, 8, 11, 15, and 29. ● Quantitative SARS-CoV-2 virus in blood at Days 3, 5, 8, and 11. 	
 ● Qualitative and quantitative polymerase chain reaction (PCR) for SARS-CoV-2 in OP swab on Day 1; Days 3, 5, 8, and 11 (while hospitalized); and Days 15 and 29 (if attends in-person visit or still hospitalized). ● Qualitative and quantitative PCR for SARS-CoV-2 in blood on Day 1; Days 3, 5, 8, and 11 (while hospitalized).

2. To evaluate the impact of study interventions on markers of inflammation and immune response.
	
 ● Proteomic analysis of plasma cytokines and markers of inflammation. ● Transcription, epigenetic, and molecular profiles of mRNA in peripheral blood mononuclear cells (PBMC). ● Phenotypic and responsiveness markers in PBMC.

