7. Women of childbearing potential must agree to either abstinence or use at least one primary form of contraception not including hormonal contraception from the time of screening through Day 29.
8. Agrees to not participate in another clinical trial (both pharmacologic and other types of interventions) for the treatment of COVID-19 through Day 29.

Exclusion Criteria:

Exclusion criteria are described in each stage-specific appendix.

Study Phase

Phase 2.

Study Sites

There will be up to approximately 20 sites throughout the US. Site selection will be determined as information becomes available about the epidemiology of COVID-19. Multiple sites will be IRB approved, but site activation will be dependent on the incidence of COVID-19 at the site.

Study Intervention

Each stage-specific appendix will detail the stage-specific study intervention.

Study Duration

The full adaptive study will last for up to 3 years.

Participant Duration

An individual subject will complete the study in about 29 days, from screening at Day -1 or 1 to follow-up on Day 29 ± 3 days.

Safety

- Given the potential severity of COVID-19 and limited information about the expected clinical course, there are no pre-specified study stopping rules.
- The Data and Safety Monitoring Board (DSMB) will have access to safety data electronically in real time.

Statistical Considerations

BET is a proof-of-concept study with the intent of identifying promising treatments that warrant future studies rather than declaring definitive efficacy after this study. The trial will enroll 100 patients per intervention and this will be compared with 100 control patients. Futility and early efficacy will be assessed after approximately 50 patients have been enrolled in the treatment and

control arms. The interim analysis will find an intervention futile if its point estimate for the primary endpoint has an odds ratio <1. An intervention can be declared efficacious early after 50 patients per arm have completed the study if the two-sided p-value is <.001. If the intervention continues to 100 patients, it will be declared promising if the final p-value is <.20 and will be considered as statistically significant if the final p-value is <.05.

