7.3 Lost to Follow-Up

A subject will be considered lost to follow-up if he or she fails to appear for all follow-up assessments. In lost to follow-up cases, attempts to contact the subject should be made and these efforts should be documented in the subject's records.

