8.3.5 Time Period and Frequency for Event Assessment and Follow-Up

For this study, all AEs that are captured as part of the study (as defined above) and SAEs occurring from the time the informed consent is signed through the Day 29 visit will be documented, recorded, and reported.

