9.3.5 Safety Analyses

Safety endpoints include death through Day 29, SAEs and Grade 3 and 4 AEs. These events will be analyzed univariately and as a composite endpoint. Time-to-event methods will be used for death and the composite endpoint. Each AE will be counted once for a given subject and graded by severity and relationship to COVID-19 or study intervention. AEs will be coded using the current version of the Medical Dictionary for Regulatory Activities (MedDRA). AEs will be presented by system organ class, duration (in days), start- and stop-date. Adverse events leading to premature discontinuation from the study intervention and serious treatment-emergent AEs will be presented either in a table or a listing.

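### AE and SAE collection closes at a visit that may fall on Day 26, while the mortality and safety endpoints run through Day 29; the unscheduled-visit rule also needs reconciling with the AE recording rules

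*Protocol*

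**What the plan says.** **Collection period.** For the AEs the study captures and for SAEs, Protocol Section 8.3.5 sets the period: "SAEs occurring from the time the informed consent is signed through the Day 29 visit will be documented, recorded, and reported". The end point is a visit, not a calendar day. The Synopsis (Participant Duration) describes an individual's time in the study as running "from screening at Day -1 or 1 to follow-up on Day 29 ± 3 days", and Table 3 gives the same ± 3 day window for the last visit.

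**Endpoints.** Table 1 lists "Cumulative incidence of SAEs through Day 29", the cumulative incidence of Grade 3 and 4 AEs over the same period, 29-day mortality, and time to death up to Day 29. Section 9.3.5 adds: "Safety endpoints include death through Day 29, SAEs and Grade 3 and 4 AEs".

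**Late awareness.** Section 8.3.6.1 asks the site to report an SAE it learns of after the study has ended, provided that the SAE occurred while the subject was participating.

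**Unscheduled visits.** Section 8.2.2 permits a contact before the next scheduled assessment when clinical considerations call for it, then states: "However, no research data is collected at this visit". Section 8.3.2 requires every SAE to go on the SAE form, and Section 8.3.6.1 requires related SAEs to be submitted within 24 hours of the site learning of them. Neither rule makes an exception by type of visit.

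**Loss to follow-up.** Section 7.3 reads: "A subject will be considered lost to follow-up if he or she fails to appear for all follow-up assessments". It continues: "In lost to follow-up cases, attempts to contact the subject should be made". Section 5.4.2 provides reminders, flexible scheduling and phone visits for all discharged subjects, and Section 9.3.2 says that efforts to limit loss to follow-up will be considerable.

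**The concern.** The horizon of the endpoints and the horizon of data collection are defined differently. The endpoints stop on a fixed day; collection stops at a visit that may come up to three days earlier. For a discharged subject phoned on Day 26, nothing in the main protocol requires anyone to find out whether a death, readmission, SAE or Grade 3 or 4 AE occurred on Days 27 to 29. The analysis cannot repair this, because the data would not exist. Events collected after Day 29 from a late visit can be left out of the analysis; events on Days 27 to 29 that were never collected cannot be added.

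The unscheduled-visit sentence matters for a related reason. Such a visit takes place because something may be wrong, and the protocol does not say whether AEs count as research data. Sites could resolve that differently. Laboratory events are the most exposed. Under the notes to Table 3, Day 15 and Day 29 visits held by phone, and all Day 22 visits, include no laboratory tests, and routine-care results may be used if they fall within the visit window. For a subject followed by phone, a test done at an unscheduled contact may be the only post-discharge source of a Grade 3 or 4 laboratory value, which is part of a listed safety endpoint.

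**Working it through.** **1. Window of the closing visit.** Inputs: target Day 29 and window ± 3 days (Synopsis; Table 3).
- Earliest: 29 − 3 = Day 26.
- Latest: 29 + 3 = Day 32.

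The protocol prints the window; Day 26 follows from it.

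**2. Largest loss against the endpoint horizon.** Endpoint horizon: Day 29 (Table 1; Section 9.3.5).
- Days not collected after a Day 26 visit: 29 − 26 = 3 (Days 27, 28 and 29).
- Share of the horizon: 3/29 = 10.3%.
- A visit on or after Day 29 loses nothing.

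**3. Average loss.** The protocol does not say how visits will spread over the window, so this needs an assumption. If the seven days 26 to 32 are equally likely:
- Share of visits before Day 29: 3/7 = 43%.
- Mean loss among those early visits: (3 + 2 + 1)/3 = 2 days.
- Mean loss over all discharged subjects: (3 + 2 + 1 + 0 + 0 + 0 + 0)/7 = 6/7 = 0.86 day, and 0.86/29 = 3.0% of the horizon.

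The range over other spreads runs from 0 (every visit on or after Day 29) to 3 days (every visit on Day 26).

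**4. Who is exposed.** Section 8.1.2.1 captures clinical status every study day while the subject is hospitalized, up to and including Day 29. The gap therefore concerns subjects already discharged.

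**5. Does the late-awareness clause close the gap?** Section 8.3.6.1 applies to SAEs that occurred during participation, and the Synopsis ends participation at the same final follow-up. For Days 27 to 29 after a Day 26 visit, the clause does not clearly apply. It also depends on the site happening to learn of the event, and it does not cover Grade 3 and 4 AEs that are not serious.

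**6. Unscheduled contacts, set side by side.**
- Section 8.2.2: no research data at the visit. The term is not defined and AEs are not excepted.
- Sections 8.3.2 and 8.3.5: all SAEs, and all AEs the study captures, are recorded from consent onwards.
- Section 8.3.1: an abnormal laboratory finding can be an AE.
- Section 8.3.6.1: the duty to report a related SAE starts when the site learns of it.

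The AE sections can reasonably be read to prevail, but the protocol does not say that they do.

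**The case against.** The strongest case against the point is that it is small. At most three days are at stake, later visits are equally permitted, inpatients are seen daily, and the window is the same in both arms. That stands, and it limits the weight of the finding without removing the mismatch.

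Several stronger readings are tempting, and the document does not support them:

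- **That Section 8.2.2 tells sites to leave AEs unrecorded.** It refers to research data, and the duties in Section 8.3 apply at every kind of contact. Section 8.2 also allows examinations to evaluate possible AEs and extraction from the hospital chart, so a value found at such a visit would sit in source records. This is a conflict to reconcile, not an established loss of data.
- **That subjects who attend some visits and miss others are never pursued.** Section 7.3 attaches contact attempts to those who miss all follow-up, but it does not confine them to that group. Sections 5.4.2 and 9.3.2 commit to retention efforts for all. The stage appendices have their own Sections 7.3 and 8.3, which are not in the text at hand.
- **That subjects seen early are counted as event-free.** Section 9.3.5 uses time-to-event methods for death and the composite safety endpoint, which can censor at last contact. Section 9.3.3 leaves missing data and informative censoring to the SAP. What the SAP cannot do is supply events that were not collected.
- **That the gap differs by arm because a working drug discharges more patients.** Table 5 has 34.6% of controls out of hospital at Day 8 (odds 0.346/0.654 = 0.529). Doubling the odds gives 1.058, or 51.4%. These are Day 8 proportions and say nothing about who is out of hospital on Days 27 to 29.

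**Conclusion.** The mismatch holds. Recording tied to a visit that may fall on Day 26 does not cover endpoints defined through Day 29. For a discharged subject seen early, the shortfall is up to 3 of 29 days (10.3%), with an average of 0.86 day over discharged subjects if visits are spread evenly. That spread is an assumption. Neither the number of early visits nor the event rate after discharge is given, so the effect on event counts cannot be calculated; it is expected to be small. The unscheduled-visit sentence is a real but lesser defect: an unreconciled conflict between Section 8.2.2 and Sections 8.3.2, 8.3.5 and 8.3.6.1. Both are worth correcting because they concern what is collected, which an analysis plan cannot change afterwards.

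**What to change.** 1. In Section 8.3.5, require AEs, SAEs, readmission and vital status to be ascertained through calendar Day 29 for every subject who has not withdrawn consent, and count events with onset up to and including Day 29. Either of two routes will do:
   - make the final-visit window Day 29 to Day 32 in the Synopsis and Table 3; or
   - keep ± 3 days and add a brief phone or record check on or after Day 29 whenever the visit is held early.
2. In Section 8.2.2, state that no research samples are taken and no scheduled efficacy assessments are done at unscheduled contacts, but that qualifying AEs and SAEs learned of there are recorded, including Grade 3 or 4 laboratory values obtained in clinical care. The ordinal score should stay off these visits: it would add off-schedule efficacy readings only in subjects with a clinical concern.

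The cost is wording changes plus either a final window of 4 days instead of 7 or a few extra calls. No new study procedure is needed.

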8.3 Adverse Events and Serious Adverse Events

8.3.1 Definition of Adverse Event (AE)

An AE is any untoward medical occurrence associated with the use of an intervention in humans, whether or not considered intervention-related. An AE can therefore be any unfavorable and unintended sign (including an abnormal laboratory finding), symptom, or disease temporally associated with the use of medicinal (investigational) product. If multiple abnormalities are part of the same clinical syndrome, they can be reported together as one AE under a unifying clinical diagnosis. For example, the diagnosis of bacterial sepsis may include hypotension, positive blood culture, and increased white blood cell count.

Any medical condition that is present at the time that the subject is screened will be considered as baseline and not reported as an AE. However, if the severity of any pre-existing (baseline) medical condition increases above baseline to severity grade 3 or 4, it should be recorded as an AE.

Given the nature of severity of the underlying illness, subjects will have many symptoms and abnormalities in vital signs and laboratory values. Only Grade 3 and 4 AEs will be captured in this trial. In addition, the following AEs will be reported:

- Any Grade 2 or higher suspected drug-related hypersensitivity reactions associated with study product administration will be reported as an AE. While there are no criteria for grading "hypersensitivity" in the Division of AIDS (DAIDS) Table for Grading the Severity of Adverse Events,² sites should use acute allergic reaction from that toxicity table.

Intermittent abnormal laboratory values or vital sign measurements common in the severely ill populations (such as electrolyte abnormalities, low blood pressure, hyperglycemia, etc.) that are part of the same clinical diagnosis (e.g., uncontrolled diabetic) can be recorded once with the worst grade for each adverse event (grade 3 and 4 only for this trial), with the start and stop date of the intermittent syndrome. If there is clear resolution of the event, and then recurrence, it should be treated as a separate adverse event. Resolution is defined as return to baseline for >48 hours (either normal if was normal at Day 1, or baseline (Day 1) grade if already an abnormality on the toxicity table at Day 1).

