8.3.2 Definition of Serious Adverse Event (SAE)

An AE or suspected adverse reaction is considered serious (i.e., is an SAE) if, in the view of either the investigator or the Sponsor, it results in any of the following outcomes:

- Death;

- A life-threatening AE;
- Inpatient hospitalization or prolongation of existing hospitalization;
- A persistent or significant incapacity or substantial disruption of the ability to conduct normal life functions; or
- A congenital anomaly/birth defect.

Important medical events that may not meet the above criteria may be considered serious when, based upon appropriate medical judgment, they may jeopardize the subject and may require medical or surgical intervention to prevent one of the outcomes listed in this definition. Examples of such medical events include allergic bronchospasm requiring intensive treatment in an emergency room or at home, blood dyscrasias, convulsions that do not result in inpatient hospitalization, or the development of drug dependency or drug abuse.

“Life-threatening” refers to an AE that at occurrence represents an immediate risk of death to a subject. An event that may cause death if it occurs in a more severe form is not considered life-threatening. Similarly, a hospital admission for an elective procedure is not considered a SAE.

All SAEs, as with any AE, will be assessed for severity and relationship to study intervention.

All SAEs will be recorded on the SAE CRF.

All SAEs will be followed through resolution or stabilization by a licensed study physician (for IND studies, a physician listed on the Form FDA 1572 as the site PI or Sub-Investigator).

All SAEs will be reviewed and evaluated by DMID and will be sent to the DSMB (for periodic review), and the IRB/IEC.

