8.3.5.1 Investigators Reporting of AEs

Information on all AEs that are captured as part of the study (as defined above) and SAEs will be reported on the appropriate CRF. These AEs and SAEs will also be described in terms of duration (start and stop date), severity, association with the study product, action(s) taken, and outcome.

Grade 1 and Grade 2 laboratory abnormalities and vitals are not expected to be reviewed, assessed or reported as adverse events.

Abnormal vital signs and clinical parameters attributed to the underlying COVID syndrome by the site PI or appropriate sub-investigator, even if meeting the Grade 3 or Grade 4 criteria, should not be reported as adverse events. This includes, but is not limited to, changes in O2 saturation, heart rate, respiration rate, & blood pressure.

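### The planned output of AEs leading to discontinuation will omit non-serious Grade 1–2 events (Grade 2 hypersensitivity aside), because the protocol never captures them as AEs

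*Protocol*

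**What the plan says.** **Capture.** Protocol section 8.3.1 sets the threshold: "Only Grade 3 and 4 AEs will be captured in this trial". The reason given is that subjects this ill will have many symptoms and abnormal values anyway. One addition is listed: "Any Grade 2 or higher suspected drug-related hypersensitivity reactions associated with study product administration will be reported as an AE".

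SAEs stand outside the threshold. Section 8.3.2 says "All SAEs will be recorded on the SAE CRF", and section 8.3.5 covers "all AEs that are captured as part of the study (as defined above) and SAEs occurring from the time the informed consent is signed", with no grade limit on the SAEs.

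Section 8.3.5.1 adds two exclusions. The first is by grade: "Grade 1 and Grade 2 laboratory abnormalities and vitals are not expected to be reviewed, assessed or reported as adverse events". The second is by attribution: "Abnormal vital signs and clinical parameters attributed to the underlying COVID syndrome by the site PI or appropriate sub-investigator" are left out "even if meeting the Grade 3 or Grade 4 criteria, should not be reported as adverse events".

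**Output.** Section 9.3.5 names death, SAEs and Grade 3–4 AEs as the safety endpoints. It then plans a table or listing of "Adverse events leading to premature discontinuation from the study intervention", alongside serious treatment-emergent AEs. No grade is attached to that output.

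**Related measures.** Table 1 has a separate safety measure counting discontinuations and temporary suspensions of product whatever the reason. It also plans an analysis over time of blood counts, creatinine, bilirubin, ALT, AST and INR, in addition to the AEs.

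**The concern.** An output of AEs leading to discontinuation can show only AEs that were recorded. If product is stopped for a Grade 2 rise in creatinine or for Grade 2 vomiting, and the event is not serious, the subject has a discontinuation but no AE. A reader of the output would not know that such subjects are missing, because nothing in 9.3.5 says that it covers a subset of grades.

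The trial exists to choose products for larger studies with about 100 subjects per arm. Events that lead clinicians to stop a product early, before they reach Grade 3, are part of what the designers of the next trial need to see. The SAP cannot repair this, because the record is not collected in the first place.

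**Working it through.** The point is one of text and the plan gives no figure to reproduce. The check takes each kind of event that could lead to a stop and follows it through the capture rules to the two outputs.

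| Event behind the stop | AE or SAE record required? | Can appear in the 9.3.5 output? | Stop counted in Table 1? |
|---|---|---|---|
| Grade 3–4 AE, not excluded by attribution | Yes (8.3.1) | Yes | Yes |
| Grade 2 suspected drug-related hypersensitivity | Yes (8.3.1) | Yes | Yes |
| SAE of any grade | Yes (8.3.2, 8.3.5) | Yes | Yes |
| Non-serious Grade 1–2 laboratory or vital-sign change | No (8.3.1, 8.3.5.1) | **No** | Yes |
| Other non-serious Grade 1–2 event | No (8.3.1) | **No** | Yes |
| Non-serious vital sign or clinical parameter attributed to COVID-19 | No, even at Grade 3–4 (8.3.5.1) | No, by deliberate exclusion | Yes |

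Three things follow.

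1. Rows four and five are the gap. No rule in the main protocol creates an AE record for them.
2. The last column is yes throughout, so the number of stops per arm is not lost.
3. The link between stop and cause is lost. Section 8.3.5.1 asks for association with product and action taken, but only for captured AEs and SAEs. Table 1 counts episodes of stopping and does not separate stops for toxicity from other stops. Section 7.2 requires a recorded reason for withdrawal from the study, which is a different event from stopping product. A case report form may carry a reason for stopping product, but the main protocol does not require one.

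**Size.** The number missing per arm would be N × d × s. Here N = 100, d is the proportion stopping product because of an adverse event, and s is the share of those events that are non-serious, Grade 1–2 and not Grade 2 hypersensitivity. The protocol gives neither d nor s, so the product cannot be evaluated.

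**The case against.** The strongest reply is that this is a scope choice and not a contradiction. The threshold is deliberate and its reason is stated. Section 9.3.5 opens with Grade 3–4 AEs and SAEs, so its later sentence can fairly be read as meaning captured AEs. Every stop is counted by arm in Table 1. A Grade 2 creatinine or ALT rise also shows up in the analysis of laboratory values over time.

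Most of this stands. The two sections can be read together without conflict, and the loss is confined to the attribution of some stops in one supportive output. What does not stand is the inference that nothing needs doing. The reason for the threshold is to avoid recording background noise, and an event that led to stopping the product is not noise. The hypersensitivity bullet shows that lower-grade events are already admitted where they matter to the product. The laboratory analysis does not connect a value to a stop, and it does not cover symptoms.

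A second reply is that the stage-specific appendices, whose text is not at hand, have their own sections on infusion halting and adverse events and might close the gap. That cannot be excluded. But sections 8.3.1 and 8.3.5.1 do not defer to the appendices on capture, whereas sections 7.1.1 and 8.2 do defer to them on their own subjects.

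A reader might also infer that prompt stopping makes a product look cleaner to the DSMB. The documents do not support that. Prompt stopping raises the any-reason discontinuation count in that arm, and section 10.1.6.2 gives the DSMB access to safety data in real time. The interim safety analyses in 9.3.7 are framed around Grade 3–4 AEs and SAEs, so a cluster of lower-grade causes might go unexplained there, but the stops would not be hidden.

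**Conclusion.** The point holds as a limited gap between what is captured and what is to be reported. As the main protocol stands, the output of AEs leading to discontinuation omits stops caused by non-serious Grade 1–2 events other than Grade 2 suspected drug-related hypersensitivity. It does not omit serious events of any grade, and the protocol does not lose count of discontinuations.

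A reader might try to put a number on the omission. Assuming 5 to 10 stops for AEs per 100 subjects, with one third to one half of them below Grade 3, gives 5 × 1/3 ≈ 2 up to 10 × 1/2 = 5 missing per arm. That only restates the assumptions. The document offers no basis for either of them, so no size is claimed here.

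The conclusion assumes that the stage-specific appendices add no capture rule for events leading to a stop.

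**What to change.** - **Section 8.3.1:** add a second bullet beside the hypersensitivity one, for example: *Any AE of any grade that leads to discontinuation or interruption of study product will be reported as an AE, subject to the exclusion in 8.3.5.1 of vital signs and clinical parameters attributed to COVID-19.*
- **Section 8.3.5.1:** in the Grade 1–2 paragraph, add an exception for abnormalities that lead to discontinuation or interruption of study product. Leave the paragraph on COVID-attributed findings as it is. It is a deliberate choice, and reversing it would mix disease course into the AE data.
- **Section 9.3.5:** state that the output is to be read with the any-reason discontinuation endpoint in Table 1, since stops for COVID-attributed findings will still appear only there.

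The added lower-grade records should stay out of the Grade 3–4 incidence endpoint and the composite, whose definitions do not change. The cost is three short edits and a few extra AE records per arm, for events the site has already acted on. No visits or samples are added. The change concerns data capture only and leaves every stopping rule untouched.
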